For a full list of study procedures, including the timing of each procedure, please refer to [Section 9.2](#) and the Schedule of Activities in [Table 2-1](#).

Statistical Considerations

Sample Size Considerations:

This is a single-arm estimation study. It is assumed that if the ORR using modified RECIST v1.1 is at least 25%, for this study (N = 100) the lower bound of the 95% CI for objective response is > 15%.

The 95% CIs for different sample sizes with an assumed ORR of 25% are presented below:

Subjects Enrolled N	Assumed ORR N (%)	95% CI %	Width %
15	4 (26.7)	7.8, 55.1	47.3
30	8 (26.7)	12.3, 45.9	33.6
40	10 (25.0)	12.7, 41.2	28.5
70	18 (25.7)	16.0, 37.6	21.6
72	18 (25.0)	15.5, 36.6	21.0
100	25 (25.0)	16.9, 34.7	17.8

Actual number of subjects enrolled in the study: a total of 72 subjects were enrolled in the study (instead of N = 100 subjects planned at the beginning of the study). Twenty-seven subjects were enrolled into cohort 1 and 15 subjects were enrolled into cohorts 2, 3, and 4.

Planned Analyses:

A futility analysis is planned for cohorts 1 and 2. Details are provided in Section [10.4.1.1](#).

The primary analysis will occur when all treated subjects had the opportunity to be followed for at least 24 weeks for tumor assessment. The final analysis will occur when all subjects complete the study. Ad hoc analyses may be conducted before the planned analyses to support program level activities.

All analyses will be descriptive with no formal hypothesis testing. Analyses will be performed separately for each cohort. In addition, analyses with cohorts pooled together for cohorts that were not terminated early due to futility will also be performed.

Efficacy analysis will be performed on the Full Analysis Set (FAS) defined as all enrolled subjects who received at least 1 dose of talimogene laherparepvec and at least 1 dose of pembrolizumab in combination and the Per Protocol Analysis Set (PPAS). The PPAS is a subset of the FAS and includes subjects who do not have important protocol deviations that are considered to have an impact on efficacy outcomes. The proportion of responders for binary endpoints will be summarized with a corresponding exact binomial 95% CI. Duration of response (DOR) among responders, and other time to event endpoints (eg, PFS and OS) will be estimated using the Kaplan-Meier method.

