3.2 Sample Size

This is a single-arm estimation study. It is assumed that if the ORR using modified RECIST v1.1 is at least 25%, for this study (N = 100) the lower bound of the 95% confidence interval for an objective response is $> 15\%$.

The 95% CIs for different sample sizes with an assumed ORR of 25% are presented below:

Subjects Enrolled N	Assumed ORR N (%)	95% CI %	Width %
15	4 (26.7)	7.8, 55.1	47.3
30	8 (26.7)	12.3, 45.9	33.6
40	10 (25)	12.7, 41.2	28.5
70	18 (25.7)	16.0, 37.6	21.6
72	18 (25.0)	15.5, 36.6	21.0
100	25 (25)	16.9, 34.7	17.8

Actual number of subjects enrolled in the study: a total of 72 subjects were enrolled in the study (instead of N = 100 subjects planned at the beginning of the study). Twenty-seven subjects were enrolled into cohort 1 and 15 subjects were enrolled into cohorts 2, 3, and 4.

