
*, iSD, * iPD
	
iSD iUE, iSD iPD iUE, iPD
	
iUE
	
Criteria for iBOR=iCR, iPR, iSD, or iPD not met. iSD must be < 77 days from date of first dose.

- **Best overall response (BOR) per modified RECIST 1.1**

BORs will be derived based on investigator assessment using modified RECIST 1.1 ([Eisenhauer et al. 2009](#)). Per RECIST 1.1, a confirmation of CR or PR by a consecutive subsequent tumor assessment will not be required for the derivation of BOR. Overall visit response assessments occurring after the start of the first subsequent anticancer therapy will not be included. With the exception of a PD observation, overall visit response assessments occurring on or after a complete or partial removal/reduction of any target lesion which contained melanoma on pathology evaluation or pathology results were unknown will not be included. The timepoint responses after initial PD will not be used to derive BOR. For the derivation of BOR, the overall visit response will be considered UE if it is SD earlier than 77 days after the date of first dose. BOR is defined as the best overall visit response up to and including the first overall visit response of PD in the following order: CR, PR, SD, PD or UE.

- **Complete response rate (iCRR) per modified irRC-RECIST**

Complete response rate (iCRR) per modified irRC-RECIST is defined as the incidence of an iBOR of iCR per modified irRC-RECIST.

- **Complete response rate (CRR) per modified RECIST 1.1**

Complete response rate (CRR) per modified RECIST 1.1 is defined as the incidence of a BOR of CR per modified RECIST 1.1.

- **Disease control rate (iDCR) per modified irRC-RECIST**

Disease control rate (iDCR) per modified irRC-RECIST is defined as the incidence of an iBOR of iCR, iPR or iSD.

- **Disease control rate (DCR) per modified RECIST 1.1**

Disease control rate (DCR) per modified RECIST 1.1 is defined as the incidence of a BOR of CR, PR or SD.

- **Duration of response (iDOR) per modified irRC-RECIST**

Duration of response (iDOR) is defined as the time from the date of an initial response that is subsequently confirmed to the earlier of iPD (see definition of iBOR per modified irRC-RECIST) or death. Subjects who have not ended their response at the time of analysis will be censored at their last evaluable tumor assessment before the start of the first subsequent anticancer therapy.

- **Duration of response (DOR) per modified RECIST 1.1**

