2. End of study date if the subject's primary reason for ending study is not "Lost to follow-up"
3. Any subsequent anti-tumor therapy initialization date
4. AE start or end date
5. Procedure and concomitant medication start/end date
6. Date of lesion assessments
7. Date of herpetic lesion swabbing
8. Visit date of vital signs; physical exam; ECOG; sample collection for local lab and central lab parameters including HSV-1
9. Date of last investigational product administration

- Objective response rate (ORR) per modified RECIST 1.1

ORR is defined as the incidence of a BOR of CR or PR per modified RECIST 1.1. Subjects who do not have any post-baseline tumor assessments will be regarded as non-responders.

- **Objective response rate (iORR) per modified irRC-RECIST**

iORR is defined as the incidence of an iBOR of iCR or iPR per modified irRC-RECIST. Subjects who do not have any post-baseline tumor assessments will be regarded as non-responders.

- **Overall survival (OS)**

Overall survival is defined as the interval from first dose to death from any cause. Subjects without an event will be censored at the last date known to be alive.

- **PD-L1 Status**

PD-L1 expression from tumor biopsy tissue samples will be reported as positive or negative. PD-L1 expression is said to have positive status if the **combined positive score (CPS)** is $\geq 1\%$, and negative status if **CPS** is $<1\%$.

- **Primary completion date**

The primary completion date is defined as the date when the last subject is assessed or receives an intervention for the final collection of data for the primary endpoints for the purpose of conducting the primary analysis, whether the study concluded as planned in the protocol or was terminated early.

The primary completion date is the date when the last subject has completed the assessments for week 24.

- **Progression-free survival (iPFS) per modified irRC-RECIST**

iPFS per modified irRC-RECIST is defined as the interval from first dose to the earlier event of iPD (per modified irRC-RECIST) or death from any cause. Subjects without an event will be censored at their last evaluable post-baseline tumor assessment if available, otherwise will be censored on study day 1.

- **Progression-free survival (PFS) per modified RECIST 1.1**

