6.1 Full Analysis Set

The Full Analysis Set (FAS) is defined as all enrolled subjects who have received at least 1 dose of talimogene laherparepvec and 1 dose of pembrolizumab in combination. The FAS will be used in the analysis of the efficacy endpoints.

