7.1 Interim Analysis and Early Stopping Guidelines

[figure not shown]
Futility analyses are not planned for cohorts 3 and 4. In cohorts 1 and 2, if there is at least 1 unconfirmed responder (PR/CR as per modified RECIST 1.1) in the first 10

subjects of a cohort, enrollment will continue in that cohort without a futility analysis. Otherwise, the DRT will oversee a futility analysis of unconfirmed response for cohorts 1 and 2, performed separately and only once for each cohort, when 15 subjects within a cohort are evaluable for response (i.e. when 15 subjects have been treated and have had the opportunity to be followed for at least 12 weeks for tumor assessment). Screening in the respective cohort will be paused during the futility analysis. The below table presents the futility criteria:

Number of Evaluable Subjects* at Futility Analysis	Minimum Number of Subjects with an unconfirmed CR/PR to Continue	Probability of Futility (%) True ORR = 25%
15	1	< 5%

* number of subjects treated and who have had the opportunity to be followed for at least 12 weeks for tumor assessment.

When the true response is 25%, the probability of futility is < 5% with at least 1 responder among 15 evaluable subjects.

A data review team (DRT) will review safety data approximately every 3 months until the data snapshot for the primary analysis to ensure no avoidable increased risk for harm to subjects. In addition, the DRT will oversee the futility analysis for each of cohorts 1 and 2. The DRT may request ad hoc meetings at any time. The DRT also has a responsibility to review and evaluate study conduct to determine whether the study integrity may affect the ability of the DRT to fulfill its primary responsibility. Therefore,

the DRT will review and evaluate eligibility/recruitment/retention of participants, management of participants, and adherence to protocol-specified criteria. The DRT will make recommendations concerning the continuation or alteration of the study on the basis of its review of the data.

The DRT will be comprised of an Amgen clinical research medical director, Amgen safety officer, and Amgen biostatistician who are external to the talimogene laherparepvec product team.

Membership, procedures, and meeting timing will be described in the study DRT charter.

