7.2 Primary Analysis

The primary analysis will occur when all subjects treated with at least 1 dose of talimogene laherparepvec or pembrolizumab have had the opportunity to be followed for at least 24 weeks for tumor assessment. The database will be cleaned and a locked database will be used for this analysis.

Before the primary analysis, ad hoc analyses may be conducted to support program level activities.

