9.1 General Considerations

Unless otherwise specified, all safety analysis will be performed on the SAS and all efficacy analysis on the FAS. All analyses will be descriptive with no formal hypothesis testing. Analyses will be performed separately for each cohort. In addition, analyses with cohorts pooled together (all cohorts pooled, cohorts 1 and 2 pooled, and cohorts 3 and 4 pooled) will be performed. Cohorts stopped for futility will not be pooled with other cohorts. Cohort data collected on the CRF will be used in the analysis. Cohort data will be checked and reviewed during the study to ensure that subjects are recorded in the correct cohort for analyses prior to database lock.

Continuous variables will be summarized by the non-missing sample size (n), mean, standard deviation, median, first and third quartiles, minimum, and maximum.

Categorical variables will be summarized by the n and percentage in each category.

Proportions and the corresponding 95% exact CIs will be provided ([Clopper and Pearson, 1934](#)).

[REDACTED], time to event endpoints will be summarized with Kaplan-Meier (KM) ([Kaplan and Meier, 1958](#)) curves, KM estimates at selected time points, KM quartiles (when estimable), the number of subjects with events and the number of subjects censored. Accompanying 2-sided 95% CI for KM quartiles ([Brookmeyer and Crowley, 1982](#)) and KM estimates will be provided.

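### A cohort stopped for futility is dropped from the pooled analyses, so the pooled ORR is then selected on the outcome it estimates

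*SAP*

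**What the plan says.** SAP 9.1 (General Considerations) plans by-cohort analyses and three pools: all four cohorts, cohorts 1 and 2, and cohorts 3 and 4. It then adds: "Cohorts stopped for futility will not be pooled with other cohorts". Protocol 10.4.2.1 has the same sentence. The protocol synopsis, under Planned Analyses, says that "analyses with cohorts pooled together for cohorts that were not terminated early due to futility will also be performed".

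The stopping rule is in SAP 7.1 and protocol 10.4.1.1 and applies to cohorts 1 and 2 only. There is no futility look "if there is at least 1 unconfirmed responder (PR/CR as per modified RECIST 1.1) in the first 10" subjects of the cohort. Otherwise one look is made when 15 subjects have been treated and could have been followed for 12 weeks, and at least 1 unconfirmed CR or PR is needed to continue. A stop therefore means 0 responders of 15.

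SAP 5 (Definitions) gives the primary endpoint: "ORR is defined as the incidence of a BOR of CR or PR per modified RECIST 1.1". For BOR by these criteria, "a confirmation of CR or PR by a consecutive subsequent tumor assessment will not be required for the derivation of BOR".

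Efficacy is analysed on the FAS, which SAP 6.1 defines as "all enrolled subjects who have received at least 1 dose of talimogene laherparepvec and 1 dose of pembrolizumab in combination". On enrolment, SAP 3.2 reports: "Twenty-seven subjects were enrolled into cohort 1 and 15 subjects were enrolled into cohorts 2, 3, and 4". Neither document says whether a cohort was stopped.

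**The concern.** The futility outcome and the primary outcome are the same variable in the same subjects: unconfirmed CR or PR by modified RECIST 1.1, assessed by the investigator. A cohort is removed when that variable is zero in all 15 subjects at the look, and never because results are good. The selection therefore pushes the pooled ORR upward, and the Clopper-Pearson interval makes no allowance for it.

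After a stop, the pool of all cohorts is no longer the FAS, and the pool of cohorts 1 and 2 is a single cohort. The primary objective concerns subjects who progressed on prior anti-PD-1 therapy, whereas the reduced pool describes the cohorts in which a response was seen. SAP 4.2 also repeats ORR and DCR by subgroup over the pooled cohorts, so the selection carries into those tables. In a study described as a single-arm estimation study, the estimate and its interval are the main product.

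**Working it through.** **Inputs.** The look at 15 subjects and the minimum of 1 responder come from SAP 7.1. The cohort sizes 27, 15, 15 and 15 (total 72) come from SAP 3.2, and the exact binomial interval from SAP 9.1. The true response rates are assumptions. It is also assumed that all 72 subjects are in the FAS, that response status is final at the look, and that a stopped cohort is dropped whole.

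**The plan's own figures.** The probability of a stop is (1 − p)^15. A responder in the first 10 only cancels the look, so it cannot add a stop. At p = 25% this is 0.75^15 = 1.3%, which agrees with the stated value of under 5%. The Clopper-Pearson interval for 18/72 is 15.5% to 36.6%, as printed in SAP 3.2.

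**Chance of a stop at lower rates.** Per cohort it is 8.7% at a true rate of 15%, 20.6% at 10% and 46.3% at 5%. The chance that cohort 1 or cohort 2 stops is 1 − (1 − q1)(1 − q2), with q1 and q2 the two cohort values.

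**Expected pooled ORR under the rule.** This is the sum over the four stop states of P(state) × E[responders kept | state] / subjects kept. The comparator is the size-weighted mean of the true rates over all 72 subjects. For rates 5/5/25/25% in cohorts 1 to 4:

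- Cohort 1, given that it is kept: (27 × 0.05 − 0.4633 × 12 × 0.05) / 0.5367 = 2.00 expected responders.
- Cohort 2, given that it is kept: 0.75 / 0.5367 = 1.40.
- Cohorts 3 and 4 together: 30 × 0.25 = 7.5.
- Neither stopped: probability 0.288, 10.90/72 = 15.1%.
- Only cohort 2 stopped: 0.249, 9.50/57 = 16.7%.
- Only cohort 1 stopped: 0.249, 8.90/45 = 19.8%.
- Both stopped: 0.215, 7.5/30 = 25.0%.
- Weighted sum: 18.8%, against (27 × 0.05 + 15 × 0.05 + 30 × 0.25) / 72 = 13.3%.

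The same calculation for other assumed rates gives:

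| True ORR, cohorts 1/2/3/4 | Chance of any stop | Pooled ORR under the rule | All-FAS ORR | Difference (points) |
|---|---|---|---|---|
| 25/25/25/25% | 2.7% | 25.1% | 25.0% | 0.1 |
| 15/15/15/15% | 16.7% | 15.6% | 15.0% | 0.6 |
| 10/10/10/10% | 36.9% | 10.9% | 10.0% | 0.9 |
| 25/10/25/25% | 21.7% | 23.0% | 21.9% | 1.1 |
| 25/5/25/25% | 47.0% | 23.3% | 20.8% | 2.5 |
| 5/5/25/25% | 71.2% | 18.8% | 13.3% | 5.5 |

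**Coverage.** By simulation (200,000 trials per scenario), the 95% exact interval from the reduced pool covers the all-FAS ORR in 96.2% to 97.9% of trials at the common rates, 93.5% at 25/5/25/25% and 87.1% at 5/5/25/25%. In the last two cases it lies wholly above the true value in 5.9% and 12.9% of trials, against 1.6% and 0.9% if all cohorts are kept.

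**One concrete trial.** Cohort 2 ends at 0/15 and the other cohorts have 15 responders. Keeping all cohorts gives 15/72 = 20.8% (12.2 to 32.0). Under the rule it is 15/57 = 26.3% (15.5 to 39.7). The lower limit passes 15%, the figure used in the sample size section, only because of the exclusion. With 72 subjects that takes 18 responders; with 57 it takes 15.

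**The case against.** The strongest reply is that the rule is prespecified, stated consistently in three places, and concerns an additional descriptive analysis. By-cohort results come first, a stopped cohort keeps its own ORR and interval, and no hypothesis is tested. The documents never say that the pool estimates a size-weighted rate over all four cohorts. The weights 27/15/15/15 are enrolment counts, not population shares, and an average of a cohort without responses and active cohorts is hard to interpret. All of this limits the harm. It does not remove the selection: prespecifying an exclusion that depends on the outcome leaves its bias in place, and the efficacy analyses are declared to be on the FAS.

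The size is also open to challenge, and these points stand:

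- At the plan's own 25% the effect is negligible. At 25/10/25/25% coverage is still about 96.7%, so under-coverage appears only where a cohort has a true rate of 5%.
- The 5.5 points assume that a stopped cohort 1 holds 27 subjects. With only 15, the keep-all expectation at 5/5/25/25% is 14.0% and the gap is 18.8 − 14.0 = 4.8 points.
- Late responses work both ways. The primary analysis waits until treated subjects "have had the opportunity to be followed for at least 24 weeks for tumor assessment". In a trial that has stopped, responses first seen after the look would be dropped too, and counting them narrows the gap. But a lower rate at the look makes a stop more likely: with 15% at the look and 25% finally in every cohort, the chance of any stop is 16.7% and the expected shift about 0.5 points.
- The exclusion does not reach everything pooled. Disposition (SAP 9.2) is overall for all enrolled subjects, and the pool of cohorts 3 and 4 is untouched. A pool of 57, 45 or 30 against 72 enrolled would give an attentive reader a hint.

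Finally, the issue may be moot. Amendment 3 of the protocol mentions no stop, and the precision table has a row for 72. That is suggestive only. Cohort 2 has exactly 15 subjects, and the 27 in cohort 1 could include subjects enrolled before 15 were evaluable.

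**Conclusion.** The concern holds. If cohort 1 or 2 was stopped, every pooled efficacy result that should contain it is selected on the primary outcome, and no planned pooled ORR restores it. Under the assumed rates the upward shift is 0.1 to 0.9 points when all cohorts share one rate and about 1.1 to 5.5 points when they differ. It is largest when one or both of cohorts 1 and 2 are nearly inactive, which is also when a stop is likely. The harm is confined to the pooled estimate and its interval: by-cohort results and the absence of formal testing are unaffected. If no cohort was stopped, the rule has no effect on the results. The change is worth making, but the study's analysis does not fail without it.

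**What to change.** Replace the sentence in SAP 9.1 and in protocol 10.4.2.1, and align the synopsis, with wording such as: *Pooled efficacy analyses include all FAS subjects in the cohorts named for that pool, whatever the futility outcome. Pooled results that omit a cohort stopped for futility are supplementary and labelled as such.* Keep the by-cohort results, and report whether any cohort met the futility criterion.

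The cost is one SAP sentence, a protocol amendment touching two places, and one extra table only if a cohort was stopped. The pooled ORR may become less favourable. Because the change would come after enrolment in an open-label study, it should be dated and both pools shown. A lighter alternative, adding the all-FAS pool only as a sensitivity analysis, would supply the missing figure but leave the selected pool as the headline. If no cohort was stopped, a statement to that effect settles the point for the results.

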7.2 Method of Treatment Assignment

All subjects enrolled will receive the same treatment.

Subjects will be assigned to 1 of 4 cohorts as follows:

- **Cohort 1 – Locally Recurrent/Metastatic - Primary Resistance**

Subjects who received anti-PD1 therapy in the locally recurrent/metastatic setting and experienced a best overall response of disease progression or stable disease prior to confirmed disease progression. The initial date of disease progression must be within 12 weeks of the last dose of a PD-1 inhibitor.

- **Cohort 2 – Locally Recurrent/Metastatic - Acquired Resistance**

Subjects who received anti-PD-1 therapy in the locally recurrent metastatic setting and experienced confirmed disease progression following a complete or partial response on anti-PD-1 therapy. The disease progression must occur within 12 weeks of the last dose of a PD-1 inhibitor.

- **Cohort 3 – Adjuvant Setting – Disease Free Interval < 6 months**

Subjects who received anti-PD-1 therapy in the adjuvant setting and experienced confirmed disease progression following a disease-free interval of < 6 months after starting the adjuvant anti-PD-1 therapy.

- **Cohort 4 – Adjuvant Setting – Disease Free Interval \geq 6 months**

Subjects who received anti PD-1 therapy in the adjuvant setting and experienced confirmed disease progression following a disease-free interval of \geq 6 months after starting the adjuvant PD-1 inhibitor.

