2.1 Objectives and Endpoints

Objectives	Endpoints
Primary	

 • To evaluate the efficacy of talimogene laherparepvec in combination with pembrolizumab as assessed by objective response rate (ORR) in subjects with unresectable/metastatic stage IIIB-IVM1d melanoma who have progressed on prior anti-PD-1 therapy 	
 • Overall response (complete response [CR]+partial response [PR]) (by investigator assessment using modified RECIST v1.1)
Key Secondary	

 • To evaluate the efficacy of talimogene laherparepvec in combination with pembrolizumab, as assessed by: 
 ○ Complete response rate (CRR), best overall response (BOR), durable response rate (DRR), duration of response (DOR), and disease control rate (DCR) ○ ORR using modified irRC-RECIST ○ Progression free survival (PFS) ○ Overall survival (OS) 	
 • Complete response, BOR, durable response, DOR and disease control, (investigator assessment using modified RECIST 1.1 and modified irRC-RECIST) and overall response using modified irRC-RECIST by investigator assessment • PFS (by investigator assessment using modified RECIST 1.1 and modified irRC-RECIST) • OS

 • To evaluate the safety of talimogene laherparepvec in combination with pembrolizumab as assessed by incidence of treatment-emergent and treatment-related adverse events, and abnormal laboratory tests in patients who have progressed on prior anti-PD-1 therapy 	
 • Incidence of treatment-emergent and treatment-related adverse events (all adverse events, grade ≥ 3 adverse events, serious adverse events, fatal adverse events, adverse events defined as events of interest), and abnormal laboratory tests

• To evaluate time to subsequent anticancer therapy	
• Time to subsequent anticancer therapy
---	---

Exploratory	
	

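### The bar on pooling futility-stopped cohorts is not limited to efficacy; if the planned pools apply to safety and cohort 1 or 2 stopped, the pooled adverse event rate would omit treated subjects because of tumour response.

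*SAP*

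**What the plan says.** SAP 9.1 sets the general rules for both kinds of analysis: "Unless otherwise specified, all safety analysis will be performed on the SAS and all efficacy analysis on the FAS". The same paragraph calls for results by cohort and continues: "In addition, analyses with cohorts pooled together (all cohorts pooled, cohorts 1 and 2 pooled, and cohorts 3 and 4 pooled) will be performed". It then adds: "Cohorts stopped for futility will not be pooled with other cohorts". Protocol 10.4.2.1 carries the same rule. The protocol synopsis, under Planned Analyses, states it ahead of its separate efficacy and safety paragraphs: "In addition, analyses with cohorts pooled together for cohorts that were not terminated early due to futility will also be performed". Neither document exempts safety.

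The trigger for stopping is response alone. Under SAP 7.1, unless a responder is seen among a cohort's first 10 subjects, "the DRT will oversee a futility analysis of unconfirmed response for cohorts 1 and 2" when 15 are evaluable. The cohort needs at least one responder to continue. Cohorts 3 and 4 have no such look.

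Three other places bear on the point:

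- Protocol 7.2: "All subjects enrolled will receive the same treatment".
- SAP 6.2: the Safety Analysis Set is every enrolled subject who had a dose of either drug, with no exclusion for futility.
- SAP 9.6.1: safety is to be analysed separately by cohort on that set. SAP 9.6.2, 9.6.3 and 9.6.8 also use by-cohort wording.

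SAP section 10 declares no departures from the protocol's analyses.

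**The concern.** Keeping a cohort without responders out of a pooled response rate is a defensible efficacy choice. The same reasoning does not carry over to toxicity. Subjects in a stopped cohort received the same two drugs, and their adverse events tell us as much about the combination as anyone else's.

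The key secondary safety objective is stated for the combination and not for particular cohorts: "To evaluate the safety of talimogene laherparepvec in combination with pembrolizumab as assessed by incidence of treatment-emergent and treatment-related adverse events". A pooled rate that follows the SAP 9.1 rule after a stop would answer that objective with a denominator chosen by tumour response, and not with the Safety Analysis Set defined in SAP 6.2. The pool of cohorts 1 and 2 would shrink to one cohort if either stopped, and would vanish if both did.

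**Working it through.** **Inputs.** SAP 3.2 says that "a total of 72 subjects were enrolled in the study": 27 in cohort 1 and 15 in each of the others (27 + 15 + 15 + 15 = 72). I assume that all were treated. SAP 7.1 gives the futility rule (0 responders among 15 evaluable) and a true response rate of 25%.

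**The plan's own figure.** The chance that a cohort meets the futility rule is q = (1 − p)^15. At p = 0.25, q = 0.75^15 = 1.34%, which agrees with the stated value of below 5%. The look at the first 10 subjects does not alter q, because 0 of 15 implies 0 of the first 10.

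**Lower response rates (my assumptions), with the two cohorts taken as independent and sharing the same rate.**

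| True response rate | One given cohort, q | At least one, 1 − (1 − q)² | Both, q² |
|---|---|---|---|
| 25% (plan) | 1.3% | 2.7% | 0.02% |
| 15% | 8.7% | 16.7% | 0.8% |
| 10% | 20.6% | 36.9% | 4.2% |

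**Size of the all-cohort safety pool.** The exact two-sided 95% upper limit for an event seen in 0 of n subjects is 1 − 0.025^(1/n).

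| Stopped | Pool n | Omitted | Zero-event upper limit |
|---|---|---|---|
| None | 72 | 0 | 5.0% |
| Cohort 2 | 72 − 15 = 57 | 15/72 = 20.8% | 6.3% |
| Cohort 1 | 72 − 27 = 45 | 27/72 = 37.5% | 7.9% |
| Both | 72 − 42 = 30 | 42/72 = 58.3% | 11.6% |

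The chance of seeing at least one case of an event with an assumed true rate of 2% is 1 − 0.98^n: 76.7%, 68.4%, 59.7% and 45.5% down the same rows.

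**Bias.** The documents give no adverse event rates for this trial, so the following rates are illustrative. Suppose cohort 1 stopped and the other cohorts have a 30% rate of grade 3 or higher events.

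- Cohort 1 also at 30%: the pooled rate is 30% with or without it. Only precision is lost.
- Cohort 1 at 40%: all treated (27 × 0.40 + 45 × 0.30)/72 = 24.3/72 = 33.8%, against 30.0% without it.
- Cohort 1 at 20%: (27 × 0.20 + 45 × 0.30)/72 = 18.9/72 = 26.3%, against 30.0% without it.

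Bias therefore needs toxicity that differs between cohorts, and it could go either way.

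**The case against.** The strongest reply is that no pooled safety table is planned, so there is nothing to distort. SAP 9.6 is the section specific to safety, and its wording is by cohort. Where the SAP wants an overall column it says so, as in SAP 9.2 for disposition and SAP 4.2 for the subgroup analyses of response and disease control. On that reading the futility bar can only affect efficacy, and the point is moot.

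This has real weight and lowers my confidence, but it does not settle the matter. SAP 9.6.1 does not say that safety is analysed only by cohort. SAP 9.1 plans by-cohort analyses and pools together, the second in addition to the first. Dropping pooled safety would depart from protocol 10.4.2.1, and SAP section 10 declares no departure. Whether a pooled adverse event rate is planned is thus unclear.

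A second reply is that the Safety Analysis Set already fixes the denominator as all treated subjects. It does define the set, but the pooling rule sits on top of it and makes no exception for safety.

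A third reply is that little depends on the outcome. This largely stands. The study is descriptive, and no decision rule uses a pooled adverse event rate. The stopped cohort would keep its own tables and stay in the listings, and adding subject counts across the four cohorts gives the overall incidence exactly.

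**Conclusion.** The point holds as a minor, conditional fault, with moderate confidence. It takes effect only if the SAP 9.1 pools cover safety and cohort 1 or 2 stopped for futility. In that event the pooled rate would rest on 57, 45 or 30 subjects instead of 72, on the assumption that everyone enrolled was treated. Under the plan's own response rate either stop is unlikely, and the case with 30 subjects is remote.

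Three stronger readings are tempting, and the documents do not support them.

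- *A cohort did stop.* A reader might infer this from enrolment of 72 against 100 planned, or from cohort 2 ending at 15, the number needed for the futility look. The documents do not attribute the shortfall to futility, and cohorts 3 and 4 also ended at 15 without any look. Nor does the 27 in cohort 1 prove that it passed, since the look waits for 12 weeks of follow-up opportunity and screening pauses only during the analysis.
- *Safety data would be lost.* They would not. Only the pooled summary is affected.
- *The pooled rate would be biased.* That depends on differences in toxicity between cohorts, for which the documents give no figures. Loss of precision is the only certain effect.

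**What to change.** Make three small edits to the SAP.

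1. In 9.1, confine the bar to efficacy, for example: *The exclusion of futility-stopped cohorts from pooling applies to efficacy analyses only. Each safety pool contains every Safety Analysis Set subject in its component cohorts.* The reference to component cohorts is needed because the pools of cohorts 1 and 2 and of cohorts 3 and 4 cannot contain the whole set.
2. In 9.6.1, say that safety is summarised by cohort and overall, with the overall summary covering all Safety Analysis Set subjects. Without this edit it stays unclear whether a pooled safety table exists.
3. In section 10, record the safety exemption as a change from protocol 10.4.2.1.

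The efficacy purpose of the bar is untouched. No new data are needed, and the most it adds is one overall column in the safety tables.
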